7.3. Investigator Site

This will be a single center study at the following location:

[REDACTED]
[REDACTED]
[REDACTED]

7.4. Investigational Device(s) and Comparator(s)

Bridge™ is an FDA-cleared medical device for the treatment of symptoms related to opioid withdrawal. Participants will be assigned to one of two interventions: active device or sham device. The sham device will be identical in appearance to the active device but will have no electrical current.

7.5. Participants

7.5.1. Inclusion Criteria

- Participant able to provide written informed consent
- Participant is 18 to 65-years old
- Participant has confirmed opioid use disorder (OUD) as defined by the *Diagnostic and Statistical Manual of Mental Disorders-5*
- Participant is entering an OUD treatment program

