7.2. Endpoints

Primary endpoints:

- Assess change in *Clinical Opiate Withdrawal Scale (COWS)* score

Secondary endpoints:

- Assess change in *Subjective Opiate Withdrawal Scale (SOWS)* score

CLINICAL INVESTIGATION PLAN

Impact of Bridge™ device as a non-pharmacological approach to treat opioid withdrawal in opioid use disorder (OUD) subjects in an inpatient treatment center

DENE0001

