8. STATISTICAL DESIGN AND ANALYSIS

This is a single site, two-arm, prospective, randomized, double-blind, sham-controlled clinical trial. The study's main outcomes are COWS and subjective opiate withdrawal scale (SOWS) scores, measured over 8 time periods: at baseline, 30, 60, 120 minutes, 2nd, 3rd, 4th, and 5th day.

The study design data results in correlated observations will be collected repeated measurements within clusters (i.e., patients). These correlations invalidate the independence assumption in commonly used univariate and multivariate statistical techniques such as t-tests and multiple linear regression. Therefore, the Generalized Estimating Equations (GEE) method was used to estimate the power and sample size, a flexible class of models that account for correlated observations and are a commonly used method for repeated data analysis. This class of model does not require the normality assumption and does not require the full specification of the joint distribution of repeated measurements. Further, the power/sample size for testing the time-averaged difference (TAD) between two means from continuous, correlated data that will be analyzed using the GEE method was calculated. Such data occur in two design types: clustered and longitudinal (repeated measurement). Time-averaged difference analysis is often used when the outcome to be measured varies with time.

The following parameter estimates are required for calculating the power:

1. Alpha (α): The probability of rejecting a true null hypothesis = 0.05
2. δ : The time-averaged difference at which the power is calculated. We estimated that the COWS time average is 2.8 for the Bridge group and 6.8 for the sham group, then $\delta = 4.0$.

The δ of 4.0 was selected such as to be conservative and taking into consideration:

Impact of Bridge™ device as a non-pharmacological approach to treat opioid withdrawal in opioid use disorder (OUD) subjects in an inpatient treatment center

DENE0001

- After the first two hours comfort medications and medication tapers may be administered to the control group thus the COWS score may be reduced
- After three days the withdrawal symptoms are anticipated to abate for both groups

The above rationale was discussed with and supported by Masimo Bridge device and OUD clinical experts.

The power was calculated for various TAD δ values 2.8, 3, 4 and 4.7 (see Figure 3).

3. σ : The standard deviation of a response (COWS): 5.047 (estimated, see Table 2 below).

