4. ρ : The base correlation between two responses on the same subject. We used the estimate calculated by the other statistician for the sample size calculation (0.40).
5. The treatment group allocation proportion is the proportion of subjects that are in the treatment group. The proportion is 1:1 (50%)
6. The number of time points at which each subject is measured: 9.
7. The time values represent the proportion of the total study time that has elapsed just before the measurement: 0, 0.003, 0.005, 0.01, 0.021, 0.25, 0.5, 0.75, 1, which are equivalent to: prior to device placement, 20 min, 30 min, 60 min, 120 min, 2nd day, 3rd day, 4th day and 5th day.

Data used for the sample size calculation was abstracted from the article by Adrian Miranda & Taca (2018)⁵.

Table 2. COWS Score Statistics Based on Article by Adrian Miranda & Arturo Taca (2018)⁵

Time (mins)	BRIDGE Group			
	Mean COWS	% Reduction	SD	n
0	20.1	0.0	6.1	73
20*	7.5	62.7	5.9	62
30	4.0	80.1	4.4	73
60	3.1	84.6	3.4	71
120	2.8	86.1	**	
1440 (Day 2)	2.1	89.6	**	
2880 (Day 3)	1.4	93.0	**	
4320 (Day 4)	1.0	95.0	**	
5760 (Day 5)	0.6	97.0		33
Average	2.8	86.0		
Pooled SD		5.047		

* 20 minutes measurement is not included in the study design; it was included from the article to enhance the estimates for the required parameters for the sample size/power calculations.

** The yellow highlighted values are estimated (extrapolated from the available data)

A sample of 32 subjects (16 in each group), each measured 9 times, achieve a power of 0.9068 when using a two-sided Wald test from a GEE analysis to test whether the time-average difference of the Bridge subjects differs from that of the sham subjects by more than 4.0 at a significance level of 0.05. The subjects are randomly split between a

[figure not shown]
Impact of Bridge™ device as a non-pharmacological approach to treat opioid withdrawal in opioid use disorder (OUD) subjects in an inpatient treatment center**DENE0001**

Bridge group and a sham group, with 50% of the subjects assigned to the Bridge group. The residual standard deviation is anticipated to be 5.04729. The measurements of each subject will be made at the following times expressed as proportions of the total study time: 0, 0.003, 0.005, 0.01, 0.021, 0.25, 0.5, 0.75, 1, which are equivalent to: prior to device placement, 20 min, 30 min, 60 min, 120 min, 2nd day, 3rd day, 4th day and 5th day. Missing values are assumed to occur completely at random (MCAR).

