Bone or Joint aches If patient was having pain previously, only the additional component attributed to opiates withdrawal is scored 0 not present 1 mild diffuse discomfort 2 patient reports severe diffuse aching of joints/muscles 4 patient is rubbing joints or muscles and is unable to sit still because of discomfort	Gooseflesh skin 0 skin is smooth 3 piloerection of skin can be felt or hairs standing up on arms 5 prominent piloerection	
Runny nose or tearing Not accounted for by cold symptoms or allergies 0 not present 1 nasal stuffiness or unusually moist eyes 2 nose running or tearing 4 nose constantly running or tears streaming down cheeks	Total Score _____ The total score is the sum of all 11 items Initials of person completing assessment: _____	

Score: 5-12 = mild, 13-24 = moderate; 25-36 = moderately severe; more than 36 = severe withdrawal

This version may be copied and used clinically.

CLINICAL INVESTIGATION PLAN

Impact of Bridge™ device as a non-pharmacological approach to treat opioid withdrawal in opioid use disorder (OUD) subjects in an inpatient treatment center
DENE0001

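### Section 8 averages the pre-placement COWS in with the outcomes and names no baseline adjustment; the primary contrast should be the post-baseline average adjusted for baseline

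*Combined protocol and SAP*

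**What the plan says.** Section 7.2 gives the primary endpoint as "Assess change in *Clinical Opiate Withdrawal Scale (COWS)* score", with no time point, model or covariate.

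Section 8 describes the main outcomes, COWS and SOWS, as "measured over 8 time periods: at baseline, 30, 60, 120 minutes, 2nd, 3rd, 4th, and 5th day". Baseline is thus the first of the outcome times. The section says that power for "testing the time-averaged difference (TAD) between two means from continuous, correlated data that will be analyzed using the GEE method was calculated". Its inputs include "The number of time points at which each subject is measured: 9", and those times are listed as "prior to device placement, 20 min, 30 min, 60 min, 120 min, 2nd day, 3rd day, 4th day and 5th day". A footnote to Table 2 explains the ninth time: the 20-minute value comes from the cited retrospective series and is not in the study schedule. The pre-placement score is in both the list of 8 and the list of 9.

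The planned difference of 4.0 is 6.8 (sham) minus 2.8 (Bridge). Section 8 ends by referring to a separate SAP, whose text is not among the documents reviewed. The text available names no baseline covariate.

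On entry, section 7.5.1 asks for consent, age 18 to 65, DSM-5 opioid use disorder and, last, "Participant is entering an OUD treatment program". Neither this list nor the exclusions in 7.5.2 mention current withdrawal or a COWS value. In Table 2 the planning cohort has a baseline mean COWS of 20.1.

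**The concern.** The baseline score is measured before randomisation and before the device is placed, so its expected difference between arms is zero. Averaged with the later visits it pulls the contrast towards zero. Used as a covariate it would instead remove part of the between-patient variation from the error. Section 8 takes the first course, at least for planning.

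The protocol also points in three directions. Section 7.2 suggests a change score. Section 8 suggests an average of raw scores that includes baseline. The 2.8 behind the planned difference is an average that excludes baseline. These are different contrasts with different power, and with 32 evaluable participants the differences are not small.

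**Working it through.** **Inputs, all from section 8.** SD σ = 5.04729; within-subject correlation ρ = 0.40; difference δ = 4.0; 16 evaluable per arm; two-sided test, with alpha described as "The probability of rejecting a true null hypothesis = 0.05".

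**Formula.** For m equally correlated measures, the variance of a participant's mean is σ²·f with f = (1 + (m − 1)ρ)/m. Then SE = σ·√f·√(2/16), and power = Φ(δ/SE − 1.96).

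**1. The plan's own figure.** With m = 9, f = 4.2/9 = 0.4667, so σ√f = 3.448 and SE = 1.219. Power = Φ(4.0/1.219 − 1.96) = 0.9068, which is the stated value.

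**2. Which rows give the 2.8.** The eight post-baseline means in Table 2 sum to 22.5, and 22.5/8 = 2.81. With the baseline row the mean is 42.6/9 = 4.73. The 2.8 is therefore a post-baseline mean.

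**3. Which rows give the SD.** Pooling 6.1 (n 73), 5.9 (62), 4.4 (73) and 3.4 (71) by degrees of freedom gives 5.047. Without the baseline row the result is 4.617. Baseline spread is therefore inside the planning SD.

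**4. Baseline kept in the average, with no difference expected there.**
- 9 times: δ = 4.0 × 8/9 = 3.56; SE = 1.219; power 0.831.
- 8 scheduled times: δ = 4.0 × 7/8 = 3.50; f = 3.8/8 = 0.475; σ√f = 3.479; SE = 1.230; power 0.812.

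**5. The 7 scheduled post-baseline visits, no covariate.** f = 3.4/7 = 0.4857; SE = 1.244; power at 4.0 is 0.896.

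**6. Unadjusted change, mean of the 7 visits minus baseline.** Taking the same SD at baseline, f = 0.4857 + 1 − 2(0.40) = 0.6857; σ√f = 4.18; power about 0.77. Subtracting baseline adds more noise than it removes at this correlation.

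**7. The 7 visits with baseline as covariate.** f = 0.4857 − r², where r is the correlation between baseline and a single post-baseline score. The documents do not give r separately, so it is shown over a range.

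| r (assumed) | f | Power at 4.0 | Equivalent gain in participants |
|---|---|---|---|
| no covariate | 0.4857 | 0.896 | – |
| 0.2 | 0.4457 | 0.919 | 0.4857/0.4457 = 1.09, about 9% |
| 0.3 | 0.3957 | 0.946 | 0.4857/0.3957 = 1.23, about 23% |
| 0.4 | 0.3257 | 0.975 | 0.4857/0.3257 = 1.49, about 49% |

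The formula ignores the small cost of estimating the covariate's slope.

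**The case against.** **The final model is not visible.** Section 8 defers to a separate SAP, and the word change in section 7.2 implies some use of baseline. A reader might infer that the trial will be analysed with baseline as an outcome visit and never adjusted for. The documents do not support that. They show it only for the description and power calculation in section 8. What stands is that the protocol names no baseline adjustment and that its sections disagree.

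**The gain depends on an unknown correlation.** The 0.40 is taken in section 8 from another statistician's estimate and describes any two responses on one subject. Mean COWS in Table 2 drops from 20.1 to 4.0 within 30 minutes, so baseline may predict later scores less well than 0.40 implies. This objection stands, and the range above replaces a single figure. At the post-baseline SD of 4.617, unadjusted seven-visit power is already 0.940, which leaves less to gain.

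**Dilution by participants not in withdrawal.** A reader might also infer that people arriving with little or no withdrawal (Appendix I starts its lowest band at 5: "Score: 5-12 = mild, 13-24 = moderate") will shrink the 4.0 by a calculable amount. The documents give no share of such arrivals. If 10%, 20% or 30% showed no difference at any visit, section 8's model would give power 0.84, 0.75 or 0.63. Section 4 describes withdrawal as following abrupt discontinuation and lasting up to two weeks, so a low scorer on arrival may develop symptoms later. If only the 30- to 120-minute visits (3 of 7) were affected, the same shares and SE would give about 0.88, 0.85 and 0.82. Section 8 also examined differences down to 2.8, and its assumed sham average of 6.8 is already in the mild band. The shares are assumptions throughout, so these figures illustrate a risk and do not measure it.

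**An entry floor.** A minimum COWS would trade recruitment, generalisability and waiting time for a benefit that cannot be sized here. Part of the recruitment text in section 7.6.1 is redacted and may describe patients' state on arrival. The case for a threshold is not made.

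**Conclusion.** The point holds for what the protocol states. Section 8 places the pre-placement COWS among the averaged outcomes, although the planned difference was built on post-baseline values. If that contrast were used, power at 32 evaluable would be about 0.81-0.83 rather than 0.907. This assumes a true post-baseline difference of 4.0, no difference at baseline, and section 8's SD and correlation. An unadjusted change score, the other reading the protocol allows, gives about 0.77.

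A post-baseline average adjusted for baseline is better than either: 0.919 to 0.975 for r from 0.2 to 0.4. Averaging post-baseline visits recovers most of the loss (0.896), and the covariate adds an amount that depends on r.

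The absence of a current-withdrawal criterion is a separate matter. It is a risk of unknown size, which a baseline covariate would not cure. It is not evidence that the trial will miss its planned difference.

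**What to change.** 1. Define the primary GEE contrast as the between-arm difference averaged over the 7 scheduled post-baseline visits (30, 60 and 120 minutes; days 2 to 5), with baseline COWS as a covariate. Do the same for SOWS with baseline SOWS.
2. Reword sections 7.2 and 8 so that both name this contrast, and confirm that the separate SAP matches. If the SAP already specifies it, only the protocol wording changes.
3. Restate the power calculation on that contrast, giving the assumed baseline-to-post correlation and a range for it.
4. Acknowledge in section 8 that the entry criteria do not require current withdrawal although the planning cohort averaged 20.1 at baseline, and report the baseline COWS distribution by arm. No entry threshold is proposed.

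The cost is wording and a rerun of the power calculation. Baseline COWS and SOWS are already collected before randomisation (section 7.1), so no visit, assessment or participant is added. The change should be fixed before unblinding.

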7.5.2. Exclusion Criteria

- Participant requires tapering from another substance at entry to treatment
- Participant is pregnant or lactating
- Participant has a history of hemophilia or psoriasis vulgaris
- Participant has a cardiac pacemaker implant device
- Participant has irritated or broken skin at the site of intended device placement
- Participant is currently participating in, or was enrolled in another clinical trial within the last 30 days
- Participant has a history of poor wound healing
- Participant has a severe autoimmune disease or uncontrolled diabetes
- Participant has an open wound/abscess infection/MRSA
- Participant has a history of a chronic pain in the last 90 days

Impact of Bridge™ device as a non-pharmacological approach to treat opioid withdrawal in opioid use disorder (OUD) subjects in an inpatient treatment center

DENE0001

- Participant has a serious medical condition which in the judgment of the principal investigator or his/her designee would make study participation unsafe, or would make intervention compliance difficult
- Participant has a psychiatric illness (bipolar disorder, schizophrenia, or other psychotic disorder, active suicidal ideation with a plan within the last month or suicide attempt)

7.5.3. Point of Randomization

After verification of eligibility, participants will be randomly assigned to one of the two groups of active or sham in equal ratios. The randomization table will be kept with the sponsor.

7.5.4. Participant Classifications

Participants will be classified according to the criteria below:

- **Screened** – Participants who are assessed for study eligibility after signing informed consent.
- **Enrolled** – Clinical trial participants who have met all inclusion criteria and do not meet any exclusion criteria and have been assigned a participant identification number.
- **Screen Failure** – Participants who do not meet all eligibility criteria. (Reason of the participant's ineligibility will be documented on a *Screening and Enrollment Log*).
- **Withdrawn** – Participants who do not complete study either because they voluntarily choose not to participate further in the study and withdraw their consent, or they are discontinued from the study per PI discretion. If a participant leaves the study prematurely or is withdrawn from the study, another participant may be recruited.
- **Lost to Follow-up** – Participant is unable to be reached for follow-up after 3 attempts. Research staff shall document on the CRF, and no further attempts will be made.
- **Completed** – Participants will be considered complete if they wear the Bridge™ for 5 days.

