2. OVERALL SYNOPSIS OF THE CLINICAL INVESTIGATION

Clinical investigation title:	Impact of Bridge™ device as a non-pharmacological approach to treat opioid withdrawal in opioid use disorder (OUD) subjects in an inpatient treatment center
Study objective(s):	The purpose of this prospective study is to investigate the efficacy of the Bridge™ device in reducing the symptoms of opioid withdrawal in a blind comparison to a sham device.
Investigational device(s):	Bridge™ active and sham devices
Number of subjects:	48 total subjects
Inclusion criteria:	
• Participant able to provide written informed consent• Participant is 18 to 65-years old• Participant has confirmed opioid use disorder (OUD) as defined by the Diagnostic and Statistical Manual of Mental Disorders-5• Participants is entering an OUD treatment program
Exclusion criteria:	
• Participant requires tapering from another substance at entry to treatment• Participant is pregnant or lactating• Participant has a history of hemophilia or psoriasis vulgaris• Participant has a cardiac pacemaker implant device• Participant has irritated or broken skin at the site of intended device placement• Participant is currently participating in, or was enrolled in another clinical trial within the last 30 days• Participant has a history of poor wound healing• Participant has a severe autoimmune disease or uncontrolled diabetes• Participant has an open wound/abscess infection/MRSA• Participant has a history of a chronic pain in the last 90 days• Participant has a serious medical condition which in the judgment of the principal investigator or his/her designee would make study participation unsafe, or would make intervention compliance difficult• Participant has a psychiatric illness (bipolar disorder, schizophrenia, or other psychotic disorder, active suicidal ideation with a plan within the last month or suicide attempt)
Groups and Randomization:	Two groups randomized at enrollment Group 1: Interventional arm - Active device Group 2: Control arm - Sham device
Duration of the clinical investigation:	2 years for enrollment completion
Study endpoint(s):	
PRIMARY:
 
• Assess change in Clinical Opiate Withdrawal Scale (COWS) score 
SECONDARY:
 
• Assess change in Subjective Opiate Withdrawal Scale (SOWS) score

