7.6.8. Device Removal

Medical staff trained and delegated will remove the Bridge device on Day 6. The device shall be disposed in a Sharps container, in accordance with Masimo's Bridge Device Training program, the Device Instructions for Use (DFU) and Operator's Manual.

If subject requests to remove the Bridge device prior to 5 days, they will be withdrawn from further study assessments and procedures, however their data collected up to the point of withdrawal may still be used for data analysis.

CLINICAL INVESTIGATION PLAN

Impact of Bridge™ device as a non-pharmacological approach to treat opioid withdrawal in opioid use disorder (OUD) subjects in an inpatient treatment center

DENE0001

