7.6.10. Study Completion

[figure not shown]
The subject is considered to have completed the study after they have worn the Bridge™ device for 5 days.

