Anticipating a 50% drop out and missing COWS evaluation rate, 48 participants (24 in each arm) should be enrolled into the study to guarantee a minimum of 32 participants who complete the COWS evaluation and the study.

Figure 3 below shows the relationships of power and sample size for the various δ s.

Figure 3. Power versus Sample Size for δ of 2.8, 3.0, 4.0 and 4.7

A separate Statistical Analysis Plan has been developed for this study.

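### Recruiting further participants after post-randomisation withdrawals, with use of withdrawn participants' data left optional, lets randomised participants be left out of the analysis at discretion

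*Combined protocol and SAP*

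**What the plan says.** Section 7.5.4 defines a withdrawn participant as one who does not complete the study, either by choice or at the principal investigator's discretion, and then states: "If a participant leaves the study prematurely or is withdrawn from the study, another participant may be recruited". It does not separate withdrawal before randomisation from withdrawal after it, sets no maximum, and does not say how the new participant relates to the one who left.

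Section 7.6.8 withdraws anyone who asks for the device to come off before 5 days, and adds that "their data collected up to the point of withdrawal may still be used for data analysis". Section 7.6.4 also withdraws a participant who is unblinded after an adverse event. For withdrawals other than requested early removal, the protocol does not say whether collected data are used.

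The synopsis gives the size as "48 total subjects". Section 8 shows that this number already carries an allowance: "Anticipating a 50% drop out and missing COWS evaluation rate, 48 participants (24 in each arm) should be enrolled into the study", so that at least 32 complete both the COWS evaluation and the study. Completion itself is defined in 7.5.4 and 7.6.10 only by wearing the "device for 5 days", with no mention of COWS.

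**The concern.** In a trial of withdrawal symptoms, people whose symptoms are not relieved have an obvious reason to leave, and relief may differ by arm. If their scores may be used or not, and a new participant may be recruited when they go, the analysed groups can drift from those randomised towards those who tolerated 5 days. Section 8 assumes that missing values are completely at random, and discretionary omission of early leavers makes that harder to defend. The randomised total is also left open against the stated 48. With a planned loss as high as 50%, this is not a rare-case provision.

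**Working it through.** **1. The plan's power.** Inputs from Section 8: difference 4.0 ("COWS time average is 2.8 for the Bridge group and 6.8 for the sham group"), SD 5.04729, correlation 0.40, 9 time points, 16 per arm, two-sided 0.05.

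- SD of a participant's time average = 5.04729 × √((1 + 8 × 0.40)/9) = 3.448.
- Standard error of the difference = 3.448 × √(2/16) = 1.219, and 4.0/1.219 = 3.281.
- Power = Φ(3.281 − 1.960) = 0.9068. This matches the stated figure.

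**2. What the 48 covers.**

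- 32 × 1.5 = 48, which is how the plan's number arises.
- Loss that 48 can absorb and still leave 32: 1 − 32/48 = 33.3%.
- Completers at the stated 50% loss: 48 × 0.5 = 24, or 12 per arm.
- Number needed for 32 completers at 50% loss: 32/(1 − 0.5) = 64.
- Power at 12 per arm: 4.0/(3.448 × √(2/12)) = 2.842, and Φ(2.842 − 1.960) = 0.811. With the 8 scheduled time points (SD of the average 3.479) it is 0.804.

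So the 48 does contain a drop-out allowance, but not one that is enough for the stated 50%.

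**3. The rules side by side.**

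| Section | Event or rule | Consequence |
|---|---|---|
| 7.5.4 | Participant leaves, or is discontinued at investigator discretion | Withdrawn; another may be recruited |
| 7.6.4 | Unblinded after an adverse event | Withdrawn |
| 7.6.8 | Asks for removal before 5 days | Withdrawn from further assessments; use of collected data optional |
| 8 | Loss allowance | Already built into 48 |

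The last two withdrawal events necessarily follow randomisation, and the first can. Nothing in these sections requires that the person who left stays in the analysis, and nothing requires that they be removed.

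**4. Size of the trial if withdrawals are followed by new recruits (illustration).** At 50% loss, one recruit per withdrawal gives 48 + 24 = 72 randomised, and recruiting until 48 complete gives 48/0.5 = 96. At 33.3% loss the corresponding numbers are 48 + 16 = 64 and 48/(2/3) = 72. The documents set none of these totals. They show only that no ceiling is stated.

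**5. Completion definitions.** Table 2 places Day 5 at 5760 min, and 5760/60 = 96 h. Five full days are 5 × 24 = 120 h, which is also the device runtime in Section 3. On that clock, someone who asks for removal in the 24 h after the Day 5 COWS has every scheduled score and is still labelled withdrawn. Conversely, someone who wears the device for 5 days but misses COWS assessments is labelled completed under 7.5.4, yet would not count towards Section 8's 32.

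**6. What leaving data out could do (illustration).** Over the 7 post-placement times, the SD of the average is 5.04729 × √((1 + 6 × 0.40)/7) = 3.518. Removing the worst fraction q of a normal distribution lowers its mean by φ(z)/(1 − q) × 3.518. If the worst sham participants were omitted in full while active-arm losses were random, q = 20% gives a shift of 1.23 and a difference of 4.0 − 1.23 = 2.77; q = 33.3% gives 1.92 and 2.08. The direction reverses if poor responders on the active device are the ones omitted.

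**The case against.** The strongest reply is that recruiting another participant excludes nobody. No section says that the person who left is dropped, Section 8 plans a GEE analysis that can take incomplete series, and if everyone randomised is kept, extra recruits add precision without bias. Investigators and care providers are blinded (7.6.4) and devices are sequentially numbered (7.1), so on the written plan discontinuation and the next allocation are decided without knowledge of the arm. The separate SAP that Section 8 mentions is not in the supplied document and may define the analysis set. All of this stands. It limits the point to what the protocol permits. It does not remove it, because 7.6.8 still makes inclusion optional, and blinding does not stop symptoms from driving who leaves.

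A reader might infer three stronger things that the documents do not support.

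- That the replacement rule itself biases the result, with the falls to about 2.8 and 2.1 as its size. Those figures come entirely from deleting sham data under assumed selection and would be the same with no replacement at all.
- That replacement after device placement should simply be banned because the 48 already allows for loss. At the stated 50% that would fix the trial at 24 completers and power of about 0.81.
- That participants with complete COWS will be discarded. That case is narrow. It assumes that Day 5 is 96 h, taken from a table summarising the cited article, and that 5 days of wear means 120 h, while the trial's own schedule is redacted. What changes is a label, since the scores already exist.

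**Conclusion.** The concern holds as a gap in the protocol's wording. Sections 7.5.4 and 7.6.8 together leave to discretion whether randomised participants who withdraw count in the analysis, on the basis of events that can depend on symptoms. The exposure is up to 24 of 48 participants at Section 8's stated 50%, a rate that combines drop-out with missing COWS. The resulting bias has no size or direction that can be derived from the documents; the totals of 72 and 96 and the differences of 2.8 and 2.1 are illustrations under assumptions.

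The related arithmetic is firm: 48 supports 32 completers only up to 33.3% loss, and at 50% it gives 24 with power of about 0.81. That power counts completers only, under the plan's own SD, correlation and difference. The mismatch between the definitions of completion is real but secondary.

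**What to change.** - **7.6.8:** change *may* to *will*, so that all COWS collected up to withdrawal are used, in the assigned arm, for every randomised participant who does not withdraw permission. State that this covers every route to withdrawal, not only requested early removal.
- **7.5.4:** state that anyone recruited after a post-randomisation withdrawal is an additional randomised participant and not a substitute, and give the maximum number randomised against the synopsis total of 48.
- **Section 8:** restate the allowance so that rate and number agree: either the 33.3% loss that 48 supports, or the 64 that a 50% loss requires.
- **7.5.4, 7.6.10 and Section 8:** reconcile the definitions of completion, so that device wear and completion of the COWS evaluation are not treated as the same thing.

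The first two changes are wording. Their cost is that incomplete series enter the GEE analysis and the sponsor gives up discretion over them. They do not recover scores never collected after withdrawal, so the missing-completely-at-random assumption still needs its own defence. The Section 8 correction costs nothing if the lower loss rate is credible, and 16 more participants (64 − 48) if 50% is kept.
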